Destroyed when notified by sponsor but not less than the minimum time required for data retention per VCU Data Retention Policy

Other

ID: HM20012696

View: SF2 - Sharing Plan

Sharing Plan

This page addresses times when investigators may be required to share information about participants or may desire to share their research information/specimens with the aim of advancing science. This page creates a plan for when and how information/specimens could be shared.

Try to anticipate all reasonably foreseeable sharing so that the consent document can also reflect that information. However, it is acceptable to amend this page later and explain either how re-consent of previously and currently enrolled participants will occur or why re-consent should not be required.

The IRB reviews this page against the consent document (if one exists) to demonstrate the ethical principle of Respect for Persons by confirming that plans for sharing do not go against what participants would understand about the use of their data/specimens.

The IRB also ensures there are adequate protections for the privacy of participants and the confidentiality of participants' data/specimens when data is shared with others.

- * Is it likely investigators could discover information about child/elder abuse or neglect that would require mandatory reporting by the investigators or staff?**

The Code of Virginia requires that most medical personnel and all employees of institutions of higher education report suspected child/elder abuse or neglect.

Yes

No
- * Will the sponsor or investigator obtain a Certificate of Confidentiality for this study?**

Certificates of Confidentiality (CoC) are issued by the National Institutes of Health (NIH), the FDA and CDC to protect identifiable research information from forced disclosure. All human subject research studies regardless of funding can qualify to receive a CoC. A CoC is automatically issued for research that was ongoing on December 13, 2016, or initiated after that date. For more information, see

<https://humansubjects.nih.gov/coc/>

- No - Will not obtain CoC for this study
- Yes - CoC has been obtained or issued automatically**
- Yes - CoC request is pending
- Yes - Plan to submit request for CoC and will amend study/ICF once status of request is known

3. * **Select the way(s) that individual-level information or biospecimens (including DNA) may be used by the VCU PI or VCU study team for other future research projects (i.e. analyses beyond/apart from the aims of this study)?**

See help text for definitions.

- Will use directly identifiable information or specimens.
(*'Directly identifiable' means that identifiers like name, medical record number, social security number, etc. are included in/attached to the dataset/specimens. Maintaining identifiable data for future research is treated as a registry by the VCU IRB. The IRB must approve the new research use in an amendment to this study or as part of a new study before the project is initiated. You will be asked more questions about this on a later page*)
- Will use de-identified or indirectly identifiable information or specimens.
(*'De-identified' means that a linkage/key code exists that links identifiers to data/specimens. When the researcher holds both the data and the key, the VCU IRB considers the subjects to be readily identifiable. Maintaining identifiable data for future research uses is treated by the IRB as a registry. The IRB must approve the new research use in an amendment to this study or as part of a new study before the project is initiated. You will be asked more questions about this on a later page*)
- Will use anonymized information or specimens.
(*'Anonymized' means that 1) no linkage/key codes exist that link identifiers to data/specimens; and 2) subjects cannot be readily identified, i.e. no direct or indirect identifiers or identifiable combinations of variables. The VCU IRB considers uses of anonymized data/specimens to not be human subject research.*)
- Will use aggregate results (summary-level results), not individual-level information or specimens.
(*The VCU IRB considers uses of aggregate data to not be human subject research because there are no individual subjects.*)
- Will contribute to an existing registry or repository
(*You will be asked more questions about this on a later page.*)
- Will not use information/specimens for purposes beyond this study.
- Not sure and will submit an amendment when known**
- Other use(s) of individual-level information in a way not listed above

4. * **Select the way(s) the VCU PI/study team may share individual-level information or biospecimens (including DNA) with other researchers who are not on this study team (i.e. for analyses beyond/apart from the aims of this study).**

See help text for definitions.

- Will share directly identifiable information or specimens with other researchers.
(*'Directly identifiable' means that identifiers like name, medical record number, social security number, etc. are included in/attached to the dataset/specimens. Maintaining identifiable data for future research uses is treated by the VCU IRB as a registry. The data recipient's use of identifiable data would require them to obtain IRB review. You will be asked more questions about this on a later page.*)
- Will share de-identified or indirectly identifiable information or specimens with other researchers.
(*'De-identified' means that a linkage/key code exists that links identifiers to data/specimens. The VCU researcher maintains the key but does not share it with any other researchers. The recipient's use of de-identified data/specimens may not be human subject research if there is documentation that the key will never be shared with the recipient, but they should check with their own IRB about review requirements. You will be asked more questions about this on a later page.*)
- Will share anonymized information or specimens with other researchers.
(*'Anonymized' means that 1) no linkage/key codes exist that link identifiers to data/specimens; and 2) subjects cannot be readily identified (i.e. no direct or indirect identifiers or identifiable combinations of variables). The VCU IRB considers uses of anonymized data/specimens by other researchers to not be human subject research, but the recipient should check with their own IRB about review requirements.*)
- Will only share aggregate results (summary-level results), not individual-level information or specimens.
(*The VCU IRB considers uses of aggregate data to not be human subject research because there are no individual subjects. The data recipient should check with their own IRB about review requirements.*)
- Will contribute to an existing registry or repository (You will be asked more questions about this on a later page.)

- Will submit data to an NIH genomic data repository (You will be asked more questions about this on a later page.)
- Will not share information/specimens with other researchers.
- Not sure and will submit an amendment when known
- Other sharing of individual-level information with other researchers

5. * Since you responded in a question above that you may use or share anonymous, individual level data, indicate why the proposed use or sharing of anonymous data/specimens is not inconsistent with what participants would have reasonably understood from the consent document about the uses of their information. (Select all that apply.)

The consent form states that after identifiers are removed, information or specimens could be used for future research studies without additional informed consent from the subject (this is a new element of consent included in consent templates as of May 2018)

6. * The Principal Investigator certifies that prior to releasing an anonymized dataset or anonymized specimens the following conditions will all be met:

- all 18 HIPAA identifiers (including all dates) will be removed;
- all indirectly identifiable data elements (unusual, rare, uncommon data) will be removed, grouped, suppressed, or otherwise transformed to no longer be readily identifiable;
- a different subject ID will be assigned than the one used for the main study and a linkage key will not be kept; and
- the PI will review the dataset/specimens to confirm that the remaining information could not be used alone or in combination with any other information to re-identify the participants represented in the data.

See help text for more information.

Yes

7. * The Principal Investigator certifies that after the study has been closed with the VCU IRB, the following conditions will be met whenever individual level research information and/or specimens are used or shared:

- The identities of participants who are represented in the dataset/specimens will not be readily ascertainable or otherwise re-identifiable by the recipient;
- If a linkage/code key is created, it will be maintained at VCU and not shared with the recipient under any circumstances;
- The PI will have no knowledge that the remaining information could be used alone or in combination with any other information to identify the individuals represented in the data; and
- The PI agrees to abide by this sharing plan even after the study has been closed with the VCU IRB.

Yes

8. If the Certificate of Confidentiality has been obtained by the PI, upload it here:

ID: HM20012696

View: SF2 - Pertinent and Incidental Findings

Pertinent and Incidental Findings

1. * Is it likely investigators could discover a participant's previously unknown condition (e.g. disease, suicidal thoughts, wrong paternity, pregnancy, genetic results, or other findings that may be of importance to health or well-being) or if a participant is engaging in illegal or reportable activities:

Yes

No

2. * Describe any possible pertinent or incidental findings stemming from research-only procedures that may be of importance to a subject's health or well-being or which may relate to illegal or reportable activities.

During screening we assess blood pressure.

During screening we assess if female participants are pregnant.

During screening we ask questions about marijuana/cannabis use and other illicit drug use.

During screening and at the beginning of a session we ask about respiratory and gastrointestinal symptoms.

3. * Explain what actions or procedures should research personnel take to handle such a discovery :

If a participant's blood pressure is high, research staff will advise the participant to talk to their own doctor and to get treatment.

If a participant is pregnant, research staff will advise the participant to seek prenatal care.

If a participant reports marijuana/cannabis use, although this is an illegal activity, the search staff will not take any actions. This study does have a certificate of confidentiality, which provides additional protections for participants.

Individuals who engage in illicit drug use in the past month will not be eligible for an in-person screen or to participate in the clinical laboratory portion of the study.

Answers given about respiratory and gastrointestinal symptoms will be compared to the participants' previous answers, and if any symptoms have increased, [name] will be asked to review the symptoms. In some cases, we may contact [name] to determine if a session can proceed.

4. * Will findings be disclosed to participants and/or any other person/group outside of the study team?

Yes

No

5. * Describe a communication plan addressing:

1. What criteria will be used to determine which pertinent and/or incidental findings will be communicated, including the following for health related findings:

- The reliability of the tests/images, such as being done in a CLIA-certified lab,
- Whether the meaning and significance of the findings are known,
- Whether the findings reveal a significant risk of a serious health condition,
- Whether there is an accepted treatment for the health condition revealed by the findings, and
- The risks both of knowing and not knowing the findings, including risks to family members from genetic testing results.

2. What information will be provided during the consent process about the plans for communicating pertinent and/or incidental findings;

3. Whether the participants will be given the option of refusing communication of some or all types of pertinent and/or incidental findings to themselves, their family members, and/or any other individuals or groups; and

4. To whom and by whom the findings will be communicated, when, and how.

Findings for blood pressure and pregnancy will be communicated to participants verbally during the in-person screening visit. These findings will only be communicated to the participant and will be communicated by the study staff conducting the screening. In the event of high blood pressure or a positive pregnancy test, the study staff will communicate this information and advise the participant to seek treatment.

The reliability of the blood pressure monitor is not known, nor is the reliability of the pregnancy tests we use.

The blood pressure measurement could reveal a significant health risk, depending on how high it is.

There is accepted treatment for high blood pressure.

There are no risks to knowing or now knowing about high blood pressure or pregnancy.

Participants do not have the option of refusing communication about their blood pressure reading or pregnancy test results.

Any adverse events may be reported to the study sponsor at FDA/NIH as needed/per their request.

Any information about adverse events reported to individuals outside of the study team will not include participants' names, DOBs, or other identifying information. Currently, the consent form indicates that such data might be shared with the study sponsor:

"Personal information about you might be shared with or copied by authorized representatives from the following organizations for the purposes of managing, monitoring and overseeing this study:

- The study Sponsor, representatives of the sponsor and other collaborating organizations
- Representatives of VCU and the VCU Health System
- Officials of the Department of Health and Human Services"

ID: HM20012696

View: SF2 - Risk Benefit Complete

Risk Benefit Complete

Protocol Progress:

- 1 INITIAL SETUP
- 2 BACKGROUND, RATIONALE & GOALS
- 3 RESEARCH PLAN
- 4 CONSENT PLAN
- 5 RISKS, PRIVACY & CONFIDENTIALITY
- 6 POPULATIONS WITH SPECIAL CONSIDERATIONS
- 7 INSTITUTIONAL REQUIREMENTS
- 8 DOCUMENTS

Click Continue below to go to the next section

ID: HM20012696

View: SF2 - Populations with Special Considerations

Populations with Special Considerations

1. * Check all participant groups that will be either
a) Specifically included in this study or
b) Discernable in the research data/specimens.

If the research is aimed at involving a broader subject population and may incidentally includes a listed population, only check the box if the participant group will be discernable in the research data/specimens. (Selections will branch)

- Children
- Emancipated minors
- Wards of the State
- Pregnant women or fetuses
- Neonates or Post-delivery Materials
- Prisoners
- Decisionally Impaired Adults
- VCU / VCUHS students or trainees
- VCU / VCU Health System employees
- Individuals with limited English proficiency
- Active military personnel
- Student populations in K-12 educational settings or other learning environments
- Members of a federally recognized American Indian and Alaska Native tribe
- None of the Above

ID: HM20012696

View: SF2 - Populations with Special Considerations Section Complete

Populations with Special Considerations Section Complete

Protocol Progress:

- 1 INITIAL SETUP
- 2 BACKGROUND, RATIONALE & GOALS
- 3 RESEARCH PLAN
- 4 CONSENT PLAN
- 5 RISKS, PRIVACY & CONFIDENTIALITY
- 6 POPULATIONS WITH SPECIAL CONSIDERATIONS
- 7 INSTITUTIONAL REQUIREMENTS
- 8 DOCUMENTS

Click Continue below to go to the next section

ID: HM20012696

View: SF2 - Study Funding

Study Funding

1. * Have you applied for funding:
- Yes
 - No
2. Is this study already funded:
- Yes
 - No
3. * Select all funding sources for this study (pending or awarded):
- Industry

- Direct Federal
- Indirect Federal
- State/Local Government
- Non-Profit - Sponsored Project
- Non-Profit - Gift
- Internal Grant
- Investigator/Departmental Funds
- None
- Other

4. Select all related proposals:

RAMS-SPOT ID# (FP/PT/PD#)	Sponsor	PI	Title	Status	Start	End
FP00006477	National Institutes of Health	[name]	Center for the Study of Tobacco Products	Funded		

5. If the following conditions are ALL met, provide the index code where ORSP will charge Single IRB (sIRB) fees associated with this review:

1. The study is externally funded (fees do not apply if the study is not funded), AND

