Reports daily use of ECIGS (≥ 3 mg/ml nicotine) or tobacco cigarettes (any frequency) AND someday use (≥ 3 days per week) of ECIGS (≥ 3 mg/ml nicotine) or tobacco cigarettes (any frequency) for the past 3 months or longer.

5. * List the study exclusion criteria:

Individuals with the following self-reported current, diagnosed medical condition(s) will be excluded automatically: heart-related conditions (e.g., recent heart attack/stroke, coronary heart disease), severe immune system disorders (e.g., HIV/AIDS, multiple sclerosis), respiratory disorders (e.g., COPD, asthma), kidney diseases, liver diseases (e.g., cirrhosis), or seizures,

Individuals with other self-reported current, diagnosed medical conditions (e.g., diabetes, thyroid disease, Lyme disease) will be considered for exclusion after consultation with the PI and medical monitor. Participants with any medical condition/medication that may affect participant safety, study outcomes, or biomarker data will be excluded based on these consultations.

Participants with self-reported current, diagnosed psychiatric conditions or who report current psychiatric treatment or psychotropic medication use will be excluded.

Individuals with past month use of cocaine, opioids, benzodiazepines, methamphetamine, or other illicit drugs. Self-report of >15 days out of the past 30 for marijuana use, or >25 days out of the past 30 for alcohol use.

Individuals who report using any other tobacco products on a weekly or more frequent basis will be excluded.

Women who are breast-feeding or test positive for pregnancy (by urinalysis at screening) will be excluded.

Individuals intending to quit tobacco/nicotine products in the next 30 days will also be excluded and referred to tobacco cessation treatment.

In addition, participants who have previously participated in a study with exactly the same manipulations of ECIG type, setting, and liquid nicotine concentration will be excluded. Individuals enrolled in HM20012738 will be excluded from the current study. Staff from this protocol will work with staff (who are also listed on this protocol) to assure that there is no cross participation between studies.

6. * Will individuals with limited English proficiency be included in or excluded from this research?

- Included
- Excluded - safety concerns if participants are unable to communicate with the study team
- Excluded - instruments/measures only validated in English**

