Overview. This study involves 60 current E-Cigarette (ECIG) only users and 60 Dual Users (ECIG + traditional tobacco cigarette) who will complete 5, within-subject, laboratory conditions that differ by the product used: 1) ECIG with low mg/ml; low watts, 2) ECIG with low mg/ml; high watts, 3) ECIG with high mg/ml; low watts, 4) ECIG with high mg/ml; high watts, and 5) own brand (ECIG or tobacco cigarette). The first ECIG 4 conditions will be Latin-square ordered and single blinded such that the participants will not know which condition is administered in each ECIG session. The last condition for all subjects will be their own brand. For ECIG users it will be their own brand ECIG. For Dual Users it will be either own brand ECIG or tobacco cigarette. To allow for comparisons between groups (ECIG vs Dual) for this own brand condition, we will aim for a majority of the Dual User sample to receive their own brand ECIG in the last session.

Participants. A total of 120 adults (ages 21-55) who currently use ECIGs only or dual ECIG and tobacco cigarettes will be enrolled. We will attempt to recruit an equal number of men and women of diverse racial/ethnic backgrounds, although this study is not intended to address gender or race/ethnic differences.

Inclusion criteria: To be included, participants must be healthy, as determined by self-report and heart rate/blood pressure (HR/BP) check, between the ages of 21-55 (as verified by photo ID), and willing to provide informed consent. They must agree to attend the lab and abstain from tobacco/nicotine as required, to use the designated products, and to follow the study protocol.

Participants must also be either A) ECIG only users [reports using ≥ 1 ml of ECIG liquid/day or approximately 1 pod/cartomizer/day of at least 3 mg/ml nicotine for the past 3 months or longer and no tobacco cigarette consumption within the past month] or B) Dual ECIG + traditional tobacco cigarette smokers [reports daily use of ECIG (≥ 3 mg/ml nicotine) or tobacco cigarettes (any frequency) AND some day use (≥ 3 days per week) of ECIGs (≥ 3 mg/ml nicotine) or tobacco cigarettes (any frequency)] use for the past 3 months or longer] who can provide a semi-quantitative urine cotinine result of 'positive' at screening (urine cotinine cassette test).

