Recruitment and Enrollment. Potential participants will be recruited by IRB-approved advertisements, as well as referral from current participants. Once initial screening is completed (either over the phone or via the internet), potentially eligible participants will earn \$10 to come to the lab for in-person informed consent, screening, and familiarization with study procedures (approximately 1.5 hrs). Prior to in-person data collection, staff will review the informed consent with potential participants to ensure they understand the study, its risks and benefits, and their rights as research participants. Following documentation of informed consent, participants will complete baseline measures to confirm eligibility and provide a urine sample that will be tested for cotinine level (to confirm current smoking status) and pregnancy (women only). Age will be verified by asking participants to provide some form of identification that includes a date of birth. We will also take pictures of their device/liquid. All study procedures will be reviewed and participants will be asked to choose the ECIG liquid flavor to be used during the four study ECIG sessions (i.e., not their own brand session). They will be given the opportunity to test four ECIG liquid flavors using the study ECIG device (tobacco, menthol, dessert, fruit) during screening. After flavor testing, participants will complete the Balloon Analogue Risk Task (BART) and the Minute Discounting Task (counter-balanced administration). Depending upon task performance, participants will receive up to \$40 in compensation for the actual amount earned at the end of the BART task.

New recruits will replace participants who do not complete the study. Accrual ends when the required number of completers (N=120) is reached.

Products. Own brand tobacco cigarette packs or ECIG liquids consistent with participant preference will be purchased locally following enrollment. For all other sessions we will provide ECIG liquid at 10mg or 30 mg nicotine and an "open system" ECIG (i.e., Kanger Sub Box Mini C) set to either 15 watts or 30 watts. Liquid flavors available will include tobacco, menthol, dessert, and fruit.

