The Minute Discounting Task is a series of hypothetical decision scenarios. Each scenario presents a choice between receiving an amount of money in the present moment or an amount of money at a later time period. These choices are differentiated by option amounts and the time frames. Participants make a choice for five decision scenarios which are automatically adjusted based upon individual responses; while there are approximately 30 potential scenarios, only five are presented to the participant. The task takes less than one minute to complete. This task will only be administered once, during the in person screening.

Physiological measures. Physiological measures are being collected primarily for participant safety during sessions. HR/BP will be measured and saved electronically using software and equipment that sounds an alarm if safety parameters are exceeded (Model 506, Criticare Systems).

Behavioral measures. Our primary behavioral measures are three behavioral choice tasks (Progressive Ratio Task, Drug Purchase Task, and Multiple Choice Procedure).

The Progressive Ratio Task (PRT) requires participants to click on a button on a computer screen 4 times to earn 1 puff of the session specific ECIG. With each additional puff the PRT requires the participant to 'work' twice as hard, in other words after each reward (a single puff) the participant will be required to press the button 8 times, 16 times, 32 times, et cetera for each successive puff. Once the participant declines to press the button for five minutes then the PRT is considered complete.

The Drug Purchase Task (DPT) includes 9 unique measures that assess hypothetical tobacco product purchasing behaviors that are specific to each population (exclusive ECIG user and Dual users) and differ by the session type (experimental ECIG or own brand session). Please see Drug Purchase Task Overview within the attached document. Exclusive users complete 2 or 3 measures for the DPT during each session. Dual users complete 3 or 5 measures for the DPT during each session. DPT measures assess single product purchasing behavior for the session specific ECIG and own brand ECIG/cigarette (1-4; Drug Purchase Task Overview) as well as cross product purchasing behavior between these three products (5-9; Drug Purchase Task Overview) at varying amounts of money. (\$0-\$10.24)

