Importantly these tasks are programmed to end early if participants report zero consumption for assessed products. Estimated time per measure is <3 min, and each measure will only be completed once per session.

The Multiple Choice Procedure (MCP) questionnaire consists of three columns and 15 rows. Ten puffs from the session specific product (session specific ECIG or Own Brand ECIG/Cigarette) will be shown in the center column while varying amounts of money (\$0.01 - \$10.24) will be presented in ascending order in right column. Participants will be instructed to circle whether they prefer puffs or money for each of the 15 choices given to them. The MCP will only be administered once, immediately following the DPT. Immediately after the questionnaire is completed, participants will be presented with one of their choices (drawn randomly) and given a 10-minute 'consumption' period in which to take puffs or receive money. After the consumption period, participants will rest for 10 minutes before either ending the session or beginning the 60-minute rest period.

Subjective measures. Repeatedly within each condition we will use the Minnesota Nicotine Withdrawal Scale and the Direct Effects of Nicotine Scale to measure nicotine withdrawal symptoms before and after each behavioral measure.

Data analysis. Subjective, physiological, DPT, MCP, and PRT data will be prepared as reported elsewhere ([name] et al., 2017; Rusted et al., 1998; [name] et al., 2010). Elasticity is estimated using an exponential demand function with nonsystematic DTP data excluded based on two criteria: trend, or whether the participant had a general decrease in consumption from the lowest to highest price; and bounce, or whether a participant reported higher consumption at sequential higher prices (Stein et al., 2015). In general, analysis will involve a mixed (between- and within-subject) ANOVA. Demographic data will be examined to determine if there are significant between-group differences on measures that may be related to study outcomes (some differences are expected, like cigarette use). Unexpected between group differences will be considered as potential covariates in the primary analysis (see Evans et al., 2006). For all ANOVAs, adjustments for sphericity violations and post-hoc testing using Tukey's HSD or planned contrasts with Bonferroni corrections will be used (Keppel, 1991). Missing data will be imputed using multiple imputation techniques (Allison, 2001).

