Participants will be using an ECIG and/or an own brand cigarette that contains nicotine. They may experience the effects of nicotine use which could include acute increases in heart rate and blood pressure, sweating, lightheadedness, dizziness, nausea, and nervousness, although these are less likely in individuals who use nicotine-containing products regularly. All of the participants are experienced ECIG users or dual (ECIG and cigarette) users.

5. * In the investigator's opinion, is there any reason to think that the participants will find the intervention offensive or embarrassing? Explain why or why not.

No.

ID: HM20012696

View: SF2 - Bio-Medical Drug / Biologic / Supplement / Other Compound Details

Bio-Medical Drug / Biologic / Supplement / Other Compound Details

1. * List all drugs and/or biologics:

Drug	Manufacturer	Types	FDA Labeling	IND Holder	IND Number
View Nicotine-containing electronic cigarette liquid (10 and 30 mg nicotine) in tobacco, menthol, dessert, and fruit flavors	AVAIL Inc	Other (Drug or Compound Not Listed Above)	Not Applicable	Not Required	
View Own brand cigarettes	Various Manufacturers	Other (Drug or Compound Not Listed Above)	Not Applicable	Not Required	
View Own brand electronic cigarette liquid	Various Manufacturers	Other (Drug or Compound Not Listed Above)	Not Applicable	Not Required	

2. * Will the Investigational Drug Service (IDS) pharmacy be utilized:

Yes

No (upload approval of the IDSP management plan below)

Not Applicable

3. * A. For each drug/biologic listed above, upload an investigator's drug brochure or package insert/FDA labeling.

B1. For drug products that require an IND, upload at least one of the following documents for verification of the IND number:

- External sponsor's protocol including IND number and signed Form FDA 1572 for the VCU Principal Investigator
- Communication from the external sponsor verifying the IND number and signed Form FDA 1572 for the VCU Principal Investigator
- VCU sponsor-investigator's FDA IND protocol including IND number
- Communication from the FDA with verification of the IND number

B2. For drug products that qualify for IND exemption under under 21 CFR 312.2(b), upload one of the following documents for each applicable drug:

- A document explaining, with protocol-specific information, how the drug's use in this study meets the relevant criteria for IND exemption under 21 CFR 312.2(b).

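### Is aiming only for a majority of Dual users on own-brand e-cigarette too weak for the own-brand comparison between groups?

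*Protocol*

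**What the plan says.** Protocol, Study Procedures, item 7, Overview: four blinded experimental e-cigarette conditions come first in Latin-square order, and own brand is always fifth. Exclusive users get their own e-cigarette. For the other group, "For Dual Users it will be either own brand ECIG or tobacco cigarette". The Overview then gives a purpose, "To allow for comparisons between groups (ECIG vs Dual) for this own brand condition", and a means, "we will aim for a majority of the Dual User sample to receive their own brand ECIG in the last session".

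Other places that bear on this:

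- **Study Population, item 3 (sample size).** 120 completers, 60 per group, for more than 80% power at p < 0.05 on the MCP and PRT breakpoints. Own-brand controls are expressly left out of that basis.
- **Study Population, item 4 (Dual entry).** One product daily, together with "someday use (≥ 3 days per week) of ECIGS (≥ 3 mg/ml nicotine) or tobacco cigarettes (any frequency"). On the natural reading every Dual user vapes regularly. Behavioral Intervention Details, item 4, agrees: "All of the participants are experienced ECIG users or dual (ECIG and cigarette) users".
- **Study Procedures, item 7, Products.** "Own brand tobacco cigarette packs or ECIG liquids consistent with participant preference will be purchased locally following enrollment". This concerns what is bought; it does not say who uses which product in session 5.
- **Same item, Behavioral measures.** For the MCP, "Ten puffs from the session specific product (session specific ECIG or Own Brand ECIG/Cigarette) will be shown in the center column". The DPT covers the session e-cigarette, own e-cigarette and own cigarette, "as well as cross product purchasing behavior between these three products".
- **SAP.** A mixed ANOVA in general terms, with nothing specific on Dual users given a cigarette in session 5.

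**The concern.** The Protocol names a comparison and then protects it with a loose, non-binding target. A majority of 60 is reached at 31, so up to 29 Dual users could smoke in session 5. No exclusive user does, so on the MCP those 29 have no counterpart in the other group. Entry criteria do not force the split, since Dual users vape regularly.

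Two things would be at stake. The first is precision, because the comparison could run at 60 against 31. The second is bias. If each Dual user simply chose, those on e-cigarette would be the ones who like it best, and the MCP measures how much money a person forgoes for puffs of that product. Putting all 60 Dual users into one own-brand mean would not help, because it would mix breakpoints for two products.

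**Working it through.** **Inputs.** 60 completers per group (Study Population, item 3). Smallest majority: 60/2 + 1 = 31. Two-sided alpha 0.05 is assumed, as sidedness is not stated. The documents give no effect size, SD or correlation, so the planned N cannot be reproduced, and results are in SD units.

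**Precision.** SE = √(1/60 + 1/n), where n is the number of Dual users on own-brand e-cigarette. The 95% half-width is 1.96 × SE. The difference detectable at 80% power is (1.960 + 0.842) × SE.

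| n | SE | SE against n = 60 | Half-width | Detectable difference |
|---|---|---|---|---|
| 60 | 0.1826 | – | 0.36 | 0.51 |
| 54 | 0.1876 | +3% | 0.37 | 0.53 |
| 45 | 0.1972 | +8% | 0.39 | 0.55 |
| 31 | 0.2212 | +21% | 0.43 | 0.62 |

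A difference with 80% power at 60 v 60 (0.5115 SD) has, at 60 v 31, power Φ(0.5115/0.2212 − 1.960) = Φ(0.352), about 64%.

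**Selection (assumed throughout).** Suppose the n Dual users with the strongest e-cigarette preference get the e-cigarette, and preference correlates r with the breakpoint. The Dual mean then shifts by r × φ(z)/p, with p = n/60 and z the normal quantile at 1 − p.

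- n = 31: p = 0.517, φ(z)/p = 0.77; shift 0.08, 0.23, 0.39 SD for r = 0.1, 0.3, 0.5.
- n = 45: p = 0.75, φ(z)/p = 0.42; shift 0.04, 0.13, 0.21 SD.
- n = 54: p = 0.90, φ(z)/p = 0.195; shift 0.02, 0.06, 0.10 SD.

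Under these assumptions, simulated rejection rates with no true group difference run from about 5% (r = 0.1, n = 54) to 42% (r = 0.5, n = 31); at r = 0 they stay at 5%.

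**Pooling all 60 Dual users.** Bias = cigarette share × product difference. With shares from 6/60 to 29/60 and assumed differences from 0.2 to 0.5 SD, it runs from 0.10 × 0.2 = 0.02 SD to 0.483 × 0.5 = 0.24 SD.

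**Where the comparison sits.** The hypotheses, under Background, Rationale and Goals, item 2, and again under Study Procedures, item 1, concern nicotine concentration, power, and the group difference in response to lower nicotine. All of these are tested in the four experimental conditions. None mentions own brand.

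**The case for a change.** The best case for a change is this. The Protocol itself treats product mix as a threat, or it would have set no target. A comparison important enough to steer session 5 deserves a number, an assignment rule and a defined analysis set. A rule cannot be added once the sessions have been run, and the wording would cost only a few sentences.

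The factual part stands: 31 meets the aim, the aim does not bind, and the visible text gives no assignment rule. The inference to a change is weaker.

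- **No stated figure is missed.** The plan claims no power for this contrast, so 60 v 60 is an outside benchmark.
- **No replacement number follows from the documents.** Whether 45, 54 or 60 is right depends on a precision the study never set for this comparison.
- **The rule may exist.** The grant file, the own-brand session questions and the purchase-task file are listed under Documents but not visible.
- **A rule that ignores preference has a price.** A Dual user may smoke daily and vape three days a week. For that person the usual product is a sensible reference, and cigarette sessions would be lost. If sessions have already been run, a new rule would also mix two assignment mechanisms within one group.
- **The large rejection rates stack three assumptions:** that preference decides the product, that assignment follows strict preference ranking, and that r is as high as 0.5. Preferring one product to another is a relative trait, while the breakpoint values one product in absolute terms, so r could well be small.

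**Conclusion.** No change to the plan follows. The wording is loose, but the effect is confined to one secondary, unpowered comparison, mainly on the MCP and on the PRT so far as it too is run on the session product. The DPT is less exposed because it treats own e-cigarette and own cigarette as separate products. The nicotine, power and group hypotheses are untouched.

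The certain cost is a 21% larger standard error if the number sits exactly at the floor of 31. It is 8% at 45, 3% at 54, and zero if every Dual user receives own-brand e-cigarette. Bias arises only if assignment follows preference and preference tracks the breakpoint, and the documents do not let its size be estimated.

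An analyst would fill the gap from the stated purpose by comparing e-cigarette recipients in the two groups, describing cigarette recipients separately, and setting the two Dual subsets' baseline characteristics side by side. Should the Dual e-cigarette subset turn out small or self-selected, the result is to be read as observational. How many Dual users should vape rather than smoke in session 5 is a balance on which reasonable statisticians would differ.
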